10.1.1 Serious Adverse Events

SAEs might not be related to the drink administration but are still required to be evaluated as above by the DSMB.

An SAE is any adverse event that:

- Results in death
- Is life-threatening for the person involved
- Is likely to result in disability or permanent invalidity
- Results in inpatient hospitalization or prolongation of existing hospitalization of a subject
- Results in a congenital anomaly or birth defect
- May, based on medical judgement, jeopardize the subject and may require medical intervention to prevent on the outcomes previously listed

Available from: https://rsc.tech-res.com/docs/default-source/safety/daids-ae-grading-table-mar2017.pdf

^b Usual Social & Functional Activities – Young Children: Activities that are age and culturally appropriate (e.g., social interactions, play activities, learning tasks, etc.).

^c Basic Self-care Functions – Young Children: Activities that are age and culturally appropriate (e.g., feeding self with culturally appropriate eating implement).

All AEs will be monitored by the investigator until a satisfactory resolution. In the event of SAEs, all clinical and laboratory investigations considered necessary by the investigator will continue until values have returned to normal. The investigator will provide the IRB with copies of all results of examinations and treatment carried out during follow up of SAEs. Additionally, all reports will be provided to the FDA and the NICHD Program Official.

10.1.2 Reporting Guidelines

If a parent/caregiver reports an AE/SAE that does not yet have a Date of Resolution and is continuous (no more than two days without interruption) across two follow-up periods, this AE/SAE will be considered one event. If more than two days pass between the reporting of symptoms, it will be considered as separate events. The total duration of the AE/SAE will be collected but only one AE/SAE Form will be completed for this particular event.

The following applies only for non-serious (typically below Grade 3) events; AEs of Grade 3 or above will follow the aforementioned policies for reporting and monitoring of serious adverse events

For non-serious events, if the AE has not resolved by the Day 14 follow-up, then depending on the type of AE (expected or unexpected) the research assistant will either continue to follow-up with the parent/caregiver or consider Day 14 as the final Date of Resolution:

- If the AE reported is listed on the Adverse Event Report Form (Codes 1-14) as a
 possible, expected AE, the research assistant will continue to follow-up the
 parent/caregiver a minimum of every 4 days until the AE resolves to record the Date of
 Resolution.
- If the AE reported is listed as "Other" (Code 15), or unexpected, and the Principal Investigator AND parent/caregiver considers the AE is not related/or is unlikely related to the intervention, the research assistant will not continue to follow-up past the Day 14 follow-up and will consider Day 14 as the final Date of Resolution.

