9.3 TELEPHONE FOLLOW-UP

On the first day that the participant drinks the yogurt, parents will schedule a phone call for 30 minutes after the drink is consumed, to ensure any adverse events are recorded. Parents will alert study personnel what time their child will consume the first yogurt and study personnel will call the participant 30 minutes after to ensure that there are no side effects from the yogurt.

These follow-up phone visits will be completed on Days 7, 11, 14 and 180 (±2 days). It is imperative that all visits be completed on a timely and regular fashion.

Generally, the Follow-Up Form will be the only form completed during the phone calls, but at times depending on parent/caregiver's report, there may be another form or two.

The follow up period includes all the time previous to the day of the interview. Any incidents that happen the day of the visit would be captured in the next Follow Up Visit.

There will be a set day that each subsequent visit should be completed for each participant. The research personnel should call all parent/caregiver's phone numbers at least one time per day in order to collect the data. If more than 3 business days have passed from the set day, the RA should alert the PI that this week's Follow-Up Form has not yet been completed. If the RA is not able to contact the participant, a Missed Visit Report Form should be completed instead and the PI should be alerted once again.

If a participant is unmasked at any point in time in during the study, PI will be alerted immediately. A Georgetown University employee in the Department of Family Medicine not associated with the study will follow up with this participant from this point on. This particular research personnel is not to discuss any information regarding this occurrence with any other personnel other than the PI.

Additional stool samples will be collected on Days 7, 14, 21 and 30 (±2 days) (Table 8).

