 the RA immediately fill out an AE Form, and if there are any SAE, alert the PI and project
 coordinator immediately.
- 5) Confirm the date and time for the next visit's call.

All interventions will be completed by week two of the trial. At day 180, participants will be queried for changes in baseline health, onset of new chronic medical conditions and non-routine medical visits in the past 6 months.

Table 8. Participant Timeline and Sample of Data Collection Schedule (N=300)

Study Day	0/1	2	7	10	11	14	21	30	180 ³
Enrollment (baseline health and demographics)	Х								
Antibiotics	→	→	→ or →	→					
Yogurt Interventions	→	→	→	→					
Fecal Sample Collection	Х		Х			Х	Х	Х	
Follow-up Data Collection			Χ		Χ	Х			Х
Daily Assessment Diary ¹	→	→	→	\rightarrow	\rightarrow	→			
16S rRNA Gene Sequences	Х		Х			Х	Х	Х	
Metatranscriptome Analysis ²	Х		Х						
PedsQL™	Х		Х			Х			
Diet Recall Diary (2 x 2 days)		→	→	→	→	→			
Clostridium difficile Analysis ²		→	→	→	→	→			
Adverse Event (AE) Reporting	→	→	→	\rightarrow	\rightarrow	\rightarrow	\rightarrow	\rightarrow	→

¹Participants keep a diary from Days 1 through 14 (collected on Days 7 and 15). Information on stool number, shape and consistency, health, use of interventions, symptomatic care, quality of life, and AEs. ²Will be conducted on all participants with clinically-defined diarrhea.

³Day 180 follow-up is required by the FDA for a safety measurement. On day 180 parents will be asked if they believe there were any additional AEs associated with the yogurt intervention that they have not reported during the previous data collection periods.

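### Section 10.1.2 enters Day 14 as the resolution date of certain non-serious adverse events that its own condition says are still unresolved

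*Combined protocol and SAP*

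**What the plan says.** Section 10.1.2 sets its condition first: "For non-serious events, if the AE has not resolved by the Day 14 follow-up". Two branches follow.

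- **Listed, expected events (Codes 1-14).** The research assistant keeps contacting the family, at least every 4 days, until the event ends, and records that date.
- **Other (Code 15) or unexpected events** that both the principal investigator and the parent consider unrelated or unlikely to be related. Here the research assistant "will not continue to follow-up past the Day 14 follow-up and will consider Day 14 as the final Date of Resolution".

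The same section, in its paragraph on events that span two follow-up periods, states: "The total duration of the AE/SAE will be collected but only one AE/SAE Form will be completed for this particular event".

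Section 10.1.1, headed Serious Adverse Events, states: "All AEs will be monitored by the investigator until a satisfactory resolution". The sentence after it turns to serious events: "In the event of SAEs, all clinical and laboratory investigations considered necessary by the investigator will continue until values have returned to normal".

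On timing, sections 9.3 and 9.3.1 place follow-up calls at Days 7, 11, 14 and 180, each ±2 days. The footnotes to Table 8 say that the daily diary, which includes adverse events, covers Days 1 to 14 and is collected on Days 7 and 15.

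**The concern.** A resolution date should mean that someone learned the event had ended. In the second branch it means that follow-up stopped. Nothing in the documents marks which meaning a given entry has, so a reader of the safety data cannot separate events that ended on Day 14 from events that were open when contact about them ceased.

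At stake are the resolution dates, the resolved or ongoing status, and any durations in the safety records. These serve the safety objective, and section 10.1 has the full DSMB evaluate adverse events of every severity. The affected group is the unexpected events. If a pattern among them later prompted a second look at relatedness, the record would show them as closed by Day 14.

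**Working it through.** The plan gives no figure to reproduce, so this is mainly a comparison of texts.

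**1. Condition against entry.** The rule is reached only if the event is unresolved at the Day 14 follow-up. The entry it prescribes is a resolution date of Day 14. Followed exactly, it stores an open event as resolved.

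**2. One field, two meanings.** For Codes 1-14 the field holds an observed end date. For the Code 15 subset it holds the end of follow-up.

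**3. Effect on a duration.** Assume that duration is taken from the recorded dates. Let onset be day *s* and true resolution day *T*.

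- Recorded duration = 14 − *s*; true duration = *T* − *s*; recorded minus true = 14 − *T*.
- If *T* is after Day 14, the record is short by *T* − 14 days. With assumed dates of onset Day 10 and resolution Day 40, it shows 14 − 10 = 4 days against 40 − 10 = 30, which is 26 days short.
- The Day 14 call may fall on Days 12 to 16 (14 ± 2), and section 9.3 has each call cover only the time before the day of the call. After a Day 12 call, an event that ends on Day 13 but is entered as Day 14 is overstated by 14 − 13 = 1 day.
- The error is therefore usually downward, but not always.

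**4. Does a later contact correct it?** At Day 180, "parents will be asked if they believe there were any additional AEs associated with the yogurt intervention that they have not reported". The events at issue have already been reported and were thought unrelated or unlikely to be related, so the question does not reach them. The same call has a wider health query, in which "participants will be queried for changes in baseline health, onset of new chronic medical conditions and non-routine medical visits". That could bring a lasting problem to light, but it is not tied to the recorded date of an earlier event. Table 8 carries adverse event reporting through Day 180, yet no text requires a status update on an open event.

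**5. Sections 10.1.1 and 10.1.2 side by side.** The monitoring sentence in 10.1.1 is worded for all adverse events, and the next sentence singles out serious ones, so it can be read as reaching non-serious events. Section 10.1.2 ends follow-up for some of these. Neither section refers to the other on this point.

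**6. How many events?** Table 9 lists 14 expected events, which matches the number of Codes 1-14; that they are the same events is an assumption. On that assumption, the Days 0-10 columns of Table 2 (Phase 1 pediatric study) contain allergies 3 + cold 2 + hives 1 + irritability 5 + lethargy 6 + umbilical hernia 1 = 18 events of other types, and 78 of listed types; 78 + 18 = 96, the table total. So 18/96 = 19% were of other types. This is not a count of affected events. That would need the share still open at Day 14 and thought unrelated or unlikely to be related by both parties, and no document gives it.

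**The case against.** The best defence is that section 10.1.2 is a deliberate exception. It says that it applies only to non-serious events, it limits calls by the research assistant, and it leaves the investigator's duty in 10.1.1 untouched. The 10.1.1 sentence also sits under the heading for serious events. A reader might infer a flat contradiction between the two sections; the documents do not support one, because a general rule and a specific exception can coexist. What remains is an unreconciled tension, and the date entered would still be final on either reading.

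It is also fair that Day 14 is not arbitrary, since diary capture ends there. That makes it a sensible last-observed date, not a resolution date.

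Some further limits stand:

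- That duration is derived from this date is a natural inference, but no section says so. The adverse event form is not in the documents and may have a separate outcome field.
- A reader might infer that the recorded duration is always a lower bound. The call window rules that out.
- A reader might infer a bias in the comparison of the arms. Section 11.3 compares adverse event rates, which do not depend on resolution dates, and section 5.2.2 does not list adverse event duration as an outcome.
- A reader might want status questions at the Day 21 and Day 30 stool collections. Table 8 schedules follow-up data only at Days 7, 11, 14 and 180, so these would be new data collection.

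**Conclusion.** The rule is wrong as written, rather than merely lacking detail: it directs staff to enter a resolution date for an event known to be unresolved. Severity is minor.

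The effect is confined to events that are non-serious, coded Other or unexpected, open at the Day 14 follow-up, and thought unrelated or unlikely to be related by both parties. For these, resolution date and status are unreliable, and any duration based on them is generally understated. The finding on dates and status rests on the text of 10.1.2 alone; the finding on durations also assumes that they are taken from the recorded date.

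A reader might be tempted to scale the Phase 1 pediatric events up to 300 children and state a number affected. The documents do not support that. Beyond the missing share, the Phase 1 children were healthy and aged 1-5, whereas this trial enrols children aged 3-12 on antibiotics for a respiratory infection.

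**What to change.** In section 10.1.2, for these events:

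- leave the Date of Resolution blank;
- record the event as ongoing at last contact, with the actual date of the last adverse event information (call or diary);
- treat any duration as censored at that date in any listing or summary that uses it.

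Using the actual date also settles whether Day 14 means the study day or the date of the call. Sections 10.1.1 and 10.1.2 should be reconciled so that it is clear which events are followed and by whom; how long follow-up lasts is for the investigators to decide.

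The cost is a sentence or two of protocol text and, if the adverse event form has no ongoing entry, a small change to the form and to REDCap, where that form is double-entered. No extra contacts are needed. The downside is that some events will remain open in the listings.

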10.2 STOPPING CRITERIA

Drink administration may be suspended if:

- Any study participant experiences death that the DSMB believes may be related to the drink administration.
- If statistically or clinically significant amount of hospitalizations occur that the DSMB believes may be related to drink administration.
- New information from outside studies reveals that it would be unethical to continue enrolling participants in the study.
- The IRB decides that the study should be stopped.
- Any serious adverse event for which a relationship with the study product cannot be ruled out.
- The occurrence of statistically or clinically significant, similar Grade 2/moderate adverse events in the study population that the DSMB or PI believe is related to the intervention.
- A statistically or clinically significant number of severe adverse events occur in the study population.

Individuals may be withdrawn from the study for any of the following:

- Adverse events; the PI will discuss AEs with the parent/caregiver, and possibly
 with the participant's physician, as needed, to determine whether the participant
 should be withdrawn from the study.
- If parents/caregivers or participants are deemed to be non-cooperative (e.g. refuse to collect stools, participate in follow-up calls or fail to complete diaries).
- If parent/caregiver is lost to follow-up, i.e. more than 1 week without contact with study personnel during the follow-up period.
- Serious adverse events related to drink administration, as determined by PI, parent/caregiver or participant's primary care physician.

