5.2 Study Outcome Measures

5.2.1 Primary Outcome Measure

The primary outcome is clinically diagnosed diarrhea anytime within 14 days of enrollment. Diarrhea is clinically defined as three or more loose stools per day for two consecutive days. This will be a dichotomous (yes or no) outcome of diarrhea during the 14-day period.

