10 ASSESSMENT OF SAFETY

We will protect participants by alerting the parents/caregivers of the common reactions to yogurt and by listing common reactions for them to monitor. We will also have close follow-up and 24-hour phone line accessibility there is a question of an allergic or idiosyncratic reaction.

Details of all adverse events reported by parents/caregivers or observed by research personnel will be recorded in the adverse event report forms. All adverse events observed will be recorded separately and all will be reported to the IRB on IRB Adverse Event forms.

In order to prevent the occurrence of adverse events, we will be stringent in enforcing our exclusion criteria, paying particular attention to the potential for an allergic reaction to strawberry or yogurt on the part of the participant.

Any child who develops evidence of allergy or hypersensitivity to any component of the investigational product will be withdrawn from the clinical study and receive no further doses of either drink. We will continue to follow these participants for safety for the remainder of the study.

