11.2 SAMPLE SIZE CONSIDERATIONS

Sample Size Calculation for the Primary Outcome: This study is a double blinded, randomized Phase II trial where subjects will be randomly assigned (1:1) to either a probiotic (BB-12) yogurt group or to a control yogurt group. The primary outcome is dichotomous, clinically diagnosed diarrhea or no diarrhea, with the rate of AAD in the general population estimated to be 20-35%. Preliminary results from the Cochrane review showed the incidence of AAD in a high dose probiotic group to be 8% versus 22% in a control group.[108] Using the Cochrane estimates, a total sample of 300 subject (150 per group) would provide a power of 0.92 for detecting a difference of 0.14 (0.22 control - 0.08 probiotic) at alpha = 0.05, 2-tailed. To allow for one interim analysis (at approximately 50% recruitment), and then adjusting the final p-value to 0.029, the power would still be 90% for detecting the difference of 0.14 in the rates of AAD. If the difference in the final rates is smaller than 0.14, such as 0.12, the resulting power would still be sufficiently large (80%) and power would be equal to 74% if the final difference in rates were equal to 0.10. While the hypothesis is one-sided (see Aim 1; we expect children receiving probiotic intervention will demonstrate less AAD than those receiving the control product), we still used a two-tailed alternative for estimating the sample size in order to be conservative. While multiple efforts are arranged to minimize loss of data, in order to obtain the primary outcome (diarrhea or no diarrhea), there still will be some participants lost to follow-up and the endpoint is unknown. Nonetheless, if the lost to follow-up rate is as high as 10% (then N=270, approximately 135 per group), power would still be 90% for detecting the difference of 0.14 and 80% for detecting a difference of 0.12.

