13.1 Data Management Responsibilities

Data Coordination will be provided by the biostatistician and the CAPRICORN research network.

The following data collection forms will be double-entered into the database:

Adverse Event Report Form (AE)

Baseline Health Status (BH)

Daily Assessment Diary (DD)

Demographic Information Form (DI)

Follow-up Form (FU)

Inclusion/Exclusion Form (IE)

Randomization Form (RZ)

Serious Adverse Event Report Form (SA)

The following data collection forms will be single-entered into the database:

Day 180 Follow-up Form (OF)

Diarrhea Report Form (DR)

Diarrhea Follow-up Form (DF)

Diet Recall Diary (DT)

Informed Consent Process Documentation (IP)

Missed Contact Report Form (MC)

PedsQL (Pediatric Quality of Life Inventory) (PQ)

Sample Collection Form (SC)

Withdrawal from Intervention Form (WI)

Yogurt Consumption Follow Up (YC)

All of these forms will be used as source documents for the study. There are 18 data collection forms in total.

Each form has a two character abbreviation that will be used throughout the study to identify the forms. The data system uses this abbreviation to identify the form. The abbreviation, plus a revision number, must be entered into the system to identify every form prior to entry. The revision number refers to changes in forms that may occur after the study starts. At the start of the study, all forms have revision number 1, i.e. the Adverse Event form is referred to as AE1.

The databases will be created using REDCap [130]. All data and forms entered will be automatically validated upon entry into REDCap (range, type, and branching logic). Using the Double Data Entry Module, the data entry system is designed for independent double data entry—where the eight specified forms would be entered twice by two different RAs. This method of data entry helps to ensure data quality and accuracy. The data coordinator will provide two separate entry records and therefore two separate databases per Study ID:

Database 1 will be considered the primary database and Database 2 will be considered the secondary database. Each RA will be given access to only 1 entry record per Study ID. Each

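### Section 10.2 lets a child be withdrawn from the study for an adverse event or for refusing stool samples, and nothing keeps that child in diarrhea follow-up to Day 14

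*Combined protocol and SAP*

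**What the plan says.** **Withdrawal.** Section 10.2 opens its list for individuals with "Individuals may be withdrawn from the study for any of the following". The reasons are adverse events (after discussion by the PI), non-cooperation, more than a week without contact, and serious adverse events related to the drink. Non-cooperation is worded "If parents/caregivers or participants are deemed to be non-cooperative (e.g. refuse to collect stools, participate in follow-up calls or fail to complete diaries". The section does not say what data are collected afterwards.

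**Primary outcome.** Section 5.2.1 defines diarrhea by counts of loose stools on two consecutive days and adds: "This will be a dichotomous (yes or no) outcome of diarrhea during the 14-day period". Section 9.3.1 says the phone visits on Days 7, 11 and 14 are where the primary data are gathered. Table 8 has the diary, including stool number and consistency, running from Day 1 to Day 14.

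**Follow-up after withdrawal.** Section 10 withdraws children with allergy or hypersensitivity from the clinical study and then says "We will continue to follow these participants for safety for the remainder of the study". Section 10.1.1 adds "All AEs will be monitored by the investigator until a satisfactory resolution", and Section 10.1.2 sets out what to do for non-serious events "if the AE has not resolved by the Day 14 follow-up". Section 13.1 lists a form titled "Withdrawal from Intervention Form (WI"), with no procedure attached.

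**Analysis.** Section 11.2 accepts that "there still will be some participants lost to follow-up and the endpoint is unknown" and responds by recomputing power at N=270. Section 11.3 promises intention to treat, with every randomized child accounted for in the assigned group, and names Fisher's exact test at 0.029. It does not say how a child with an unknown outcome is counted.

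**The concern.** Section 10.2 does not separate three things: stopping the yogurt, stopping stool sampling, and ending outcome collection. A family that declines stool samples but still keeps the diary and answers calls can supply the primary outcome, yet may be removed from the study. The same holds for a child withdrawn for an adverse event other than diarrhea whose diarrhea would begin later in the 14 days. In both cases an outcome that could have been obtained becomes unknown because of a study rule.

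The intention-to-treat sentence in Section 11.3 needs those outcomes. Assigning a child to the randomized group does not supply a yes or no for the Fisher table. Sections 11.2 and 11.3 also point to different denominators, 270 and all 300 randomized.

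**Working it through.** **1. Which withdrawal reasons lose an obtainable outcome?**

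| Reason in Section 10.2 | Does it remove the source of the primary outcome? | Is later follow-up promised elsewhere? |
|---|---|---|
| Refuses stool samples | No: diary and calls remain | No |
| Adverse event, not allergy | No | Only for the event already reported (10.1.1, 10.1.2) |
| Allergy or hypersensitivity | No | Yes, for safety (Section 10) |
| Refuses calls or diary | Mostly yes | No |
| More than a week without contact | Mostly yes | No |

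The gap is therefore in the first two rows. Loose stools already present at withdrawal are partly covered by the adverse-event rules. Diarrhea that starts after withdrawal is not.

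**2. The plan's own figure for unknown outcomes.** Section 11.2 gives 90% power at 135 per group for 0.22 versus 0.08. With the pooled normal approximation, two-sided alpha 0.05 and mean rate 0.15:

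- SE under the null = √(2 × 0.15 × 0.85 / 135) = 0.0435
- SE under the alternative = √((0.22 × 0.78 + 0.08 × 0.92) / 135) = 0.0426
- Power = Φ[(0.14 − 1.96 × 0.0435) / 0.0426] = 0.90

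The figure reproduces. It drops children with unknown outcomes from the denominator, so Section 11.2 implies an analysis of known outcomes.

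**3. Does the handling of unknown outcomes matter?** Inputs: 150 per arm; 10% unknown, the upper loss figure in Section 11.2, assumed equal by arm (15 each); threshold 0.029. Known cases are 0.22 × 135 = 29.7, taken as 30, and 0.08 × 135 = 10.8, taken as 11. For the 0.12 difference that Section 11.2 also considers, I assume 22% versus 10%: 0.10 × 135 = 13.5, taken as 14. Two-sided Fisher exact p-values, control versus BB-12:

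| Rule | 22% vs 8% | 22% vs 10% |
|---|---|---|
| Known outcomes only | 30/135 vs 11/135: 0.002 | 30/135 vs 14/135: 0.013 |
| Unknown = no diarrhea | 30/150 vs 11/150: 0.002 | 30/150 vs 14/150: 0.014 |
| Unknown = diarrhea, both arms | 45/150 vs 26/150: 0.014 | 45/150 vs 29/150: 0.044 |

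Taking 13 BB-12 cases instead of 14 gives 0.007, 0.008 and 0.031. Taking the 0.12 difference as 20% versus 8% (27 and 11 of 135) gives 0.008, 0.009 and 0.038. The pattern is the same.

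**4. Tipping points at planned rates.** If no missing control child is a case, significance holds with 4 of 15 missing BB-12 children as cases (30/150 vs 15/150, p=0.023) and is lost with 5 (30/150 vs 16/150, p=0.036). If 3 of 15 missing controls are cases, it holds with 6 (33/150 vs 17/150, p=0.020) and is lost with 7 (33/150 vs 18/150, p=0.031).

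**5. Smaller loss.** With 8 unknown per arm (about 5%) at 22% versus 10%, known cases are 31/142 and 14/142. Counting every unknown child as diarrhea gives 39/150 vs 22/150, p=0.021, which is still below 0.029.

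**The case against.** The clause is permissive, and adverse-event cases are discussed one by one. Elsewhere withdrawal does not end contact: allergy withdrawals are followed for the rest of the study, and the only withdrawal form listed concerns the intervention. Diarrhea is itself a listed adverse event in Table 9, with the same definition as the primary outcome, and Table 8 runs adverse-event reporting to Day 180. Safety follow-up would therefore probably capture the primary event where it takes place. All of this stands, and it means that loss of outcomes is possible rather than certain. It does not fill the gap, because none of these passages expressly extends to non-allergy withdrawals or to stool refusal. The differing use of the word withdrawn also leaves staff without a clear instruction.

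On the analysis side, the N=270 calculation already points to a known-outcomes analysis. What is missing there is mostly a statement of that choice and its reconciliation with the intention-to-treat sentence.

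A reader might infer that the choice of rule alone can decide the trial. The figures do not support that. The two ordinary rules agree in every scenario. The switch needs every unknown child counted as diarrhea, at the full 10% loss and the smaller difference, or missing cases concentrated in the BB-12 arm. A reader might also infer that the rule would be picked after the data are seen. The documents do not say so; the trial is double-blind, and a rule can still be fixed before unblinding.

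**Conclusion.** The point holds as a design weakness worth correcting. Section 10.2, used as written, can make obtainable 14-day outcomes unknown, and no other section prevents this for stool refusal or for non-allergy adverse events. Its size is not quantified, because the documents give no frequency for such withdrawals. The p-values above rest on the loss-to-follow-up figure in Section 11.2 and an assumed equal split by arm. They do not measure the effect of Section 10.2.

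The missing rule in Section 11.3 is secondary. Under the ordinary rules the result is robust; it crosses 0.029 only under the extreme assumptions shown. No inflation of the type I error is claimed, since that would need strongly unequal loss between arms in a blinded trial.

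**What to change.** **Main change.** Reconcile Sections 10, 10.2 and 13.1 so that stopping product or stool sampling is recorded separately from ending outcome collection. This need not alter when product is stopped. State that the diary and scheduled calls continue through Day 14 for every randomized child unless consent for follow-up is withdrawn, and that stool refusal alone does not end collection of the primary outcome.

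**Secondary change.** Before unblinding, state in Section 11.3 that the primary Fisher test uses children with a known outcome, as N=270 in Section 11.2 implies, and that any child who met the definition before leaving counts as a case. Add a tipping-point sensitivity analysis over all 300 randomized, which reconciles this with the intention-to-treat sentence.

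**Cost.** Wording in a few sections and one sensitivity table. There are no added visits and no change to the primary test. The downside is that staff keep contacting some reluctant families for up to two weeks.
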